Patients will come off study at the time of radiographic (CT and/or bone scintigraphy) disease progression, with progression being defined only AFTER the first 3-month staging evaluation, at the time of undue toxicity (as defined below), or at the discretion of the patient and treating physician that continuing treatment is not in the best interest of the patient and/or that other standard therapies for prostate cancer are warranted due to symptomatic progression. Patients should be discouraged from discontinuing protocol treatment for PSA rise only. NaF and FLT PET/CT scans will be investigational and will not be used for making individual subject treatment decisions with respect to progression necessitating continuing or discontinuing protocol treatment. However, findings on NaF or FLT PET/CT that might pose medical risk to individual subjects will be communicated to the treating physician such that dedicated clinical imaging/intervention could be pursued, if necessary. Such findings on NaF or FLT PET/CT, by themselves, will not be used to define disease progression necessarily requiring patients to come off trial. Patients who, in the discretion of the treating physician, appear to be benefiting (e.g. declining serum PSA and/or

improvement in symptoms despite new radiographic lesions), may continue in protocol treatment/observation after discussion with the PI and study sponsor. Patients will continue to have blood drawn for immune studies, as per study calendar, up to one year after screening, even if off study prior to that time. Patients who undergo an initial research biopsy and/or NaF/FLT PET scan should also undergo the subsequent scans, as long as they are willing, even if they are off study prior to Month 3. In particular, evaluations performed at 6-month time point should be performed even if off-study prior to that time, if feasible. All subjects who have not come off study earlier for these reasons will come off study at the end of one year.

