A treatment-limiting toxicity will be defined as any Grade 3 or greater toxicity (using the NCI Common Terminology Criteria version 4, Appendix C), or a specific Grade 2 event as described below that affects agent dosing, with an attribution of at least possibly related to the study or treatment procedures, and occurring between the pre-study visit and within one month of the final study vaccine treatment or within 90 days of the last treatment with pembrolizumab (whichever is later). In general, if a patient develops Grade 3 toxicity with an attribution of at least possibly related to treatment (vaccine and/or pembrolizumab), the treatment schedule will be held until the toxicity resolves to Grade 1 or less. There will be no dose reductions due to adverse events. If a patient develops a second Grade 3 event both believed at least possibly due to treatment, or any Grade 4 event, no further treatments will be given. The patient will remain on study, however, with collection of radiographic and laboratory data as per protocol. The rationale for this is that patients could continue to benefit in terms of anti-tumor response and this could in fact be related to the development of other autoimmune toxicities. If the adverse event occurs during the initial 12 weeks (Arm 1) or 24 weeks (Arm 2) of treatment, a treatment delay of up to one week will be permitted, with the expectation that the event resolve to < grade 2 for retreatment, and that subsequent treatment will resume at the original study intervals. A delay > 1 week will result in a skipped dose/treatment. While rare overall, autoimmune events observed following pembrolizumab treatment of patients with melanoma typically resolved and did not necessarily lead to discontinuation of treatment.

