4. Subjects will be observed for an additional 30 minutes for unanticipated adverse events. Vital signs (temperature, heart rate and blood pressure) will be assessed and recorded by the staff prior to, and at the end of, the treatment period.

P. DAY 148 – (21 +/- 3 days after day 127 visit):

1. Physical examination, symptoms assessment, and ECOG performance score.
2. Blood draw for CBC, chemistry panel, serum PSA and PAP

ARM 2 SUBJECTS ONLY – Anti-PD-1 #4:

3. Pembrolizumab 2 mg/kg administered intravenously over 30 minutes
4. Subjects will be observed for an additional 30 minutes for unanticipated adverse events. Vital signs (temperature, heart rate and blood pressure) will be assessed and recorded by the staff prior to, and at the end of, the treatment period.

Q. 6-month Follow-up – Day 169 (21 days +/- 3 days after day 148 visit)

1. Physical examination, symptoms assessment, and ECOG performance score
2. Blood draw for CBC, chemistry panel, serum PSA and PAP

3. CT scan of abdomen/pelvis and bone scintigraphy (can be performed +/- 7 days of this visit)
 4. 10 ml peripheral blood (red-top tubes) for sera to evaluate antibody responses, and 20 ml peripheral blood (green-top heparinized tubes) for CTC analysis
 5. Leukapheresis (~1.0 blood volume, 100 mL collection) for T-cell response evaluation (can be performed +/- 7 days of this study visit)
- NOTE: For patients unable to undergo leukapheresis at this time point, a 200-cc blood draw may be substituted (twenty 10-mL green-top heparinized tubes).

R. 9-Month Follow-up (84 days +/- 10 days following 6-month study visit)

1. Physical examination, symptoms assessment, and ECOG performance score.
2. Blood draw for CBC, chemistry panel, serum PSA and PAP
3. 10 ml peripheral blood (red-top tubes) for sera to evaluate antibody responses, and 100 ml peripheral blood (green-top heparinized tubes) for T-cell response evaluation and CTC analysis
4. CT scan of abdomen and pelvis, bone scintigraphy (can be performed +/- 7 days of this visit)

S. 12-Month Follow-up (84 days +/- 10 days following 9-month study visit)
OFF-STUDY Visit

1. Physical examination, symptoms assessment, and ECOG performance score.
2. Blood draw for CBC, chemistry panel, serum PSA and PAP
3. 10 ml peripheral blood (red-top tubes) for sera to evaluate antibody responses, and 100 ml peripheral blood (green-top heparinized tubes) for T-cell response evaluation and CTC analysis

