4. CT scan of abdomen and pelvis, bone scintigraphy (can be performed +/- 7 days of this visit, and does not need to be repeated for off-study visit if progression of disease already confirmed within 1 month)

T. Long-term Follow-Up

1. Subjects will be contacted by telephone (if not already being seen in clinic) annually for 2 years following the last DNA vaccination to collect clinical information to identify any potential long-term risks. This information has been requested by FDA for all gene delivery trials to assess potential long-term risks. The specific information to be collected annually will include:
 - Date of contact
 - Current medications
 - Hospitalizations (dates and reasons for hospital admission)
 - Stage of prostate cancer, treatments for prostate cancer, and recent serum PSA level
 - New cancer diagnoses
 - New autoimmune disorders
 - New hematologic or neurologic disorders
 - Other new medical diagnoses

- Date of death if patient deceased

EXTENDED TREATMENT COHORT – ARM 3:

U. Prescreen / Eligibility (performed within 6 weeks of Day 1)

1. Confirm potential eligibility by history, pathology, diagnosis; no exclusions by history
2. CT scan of abdomen and pelvis (CT of chest as clinically indicated), bone scan
3. Sign consent form
4. Evaluation of CBC, chemistry panel, serum prostate specific antigen (PSA), serum PAP, and serum testosterone.

V. Pre-Treatment Evaluations (within 4 weeks of Day 1; can coincide with prescreen evaluation)

1. Physical examination, symptoms assessment, and ECOG performance score
2. Baseline research leukapheresis (50-100 mL approximate total volume, for immunological monitoring) – to take place within 4 weeks prior to day 1.
NOTE: For patients unable to undergo leukapheresis at this time point, a 200-cc blood draw may be substituted (twenty 10-mL green-top heparinized tubes).
3. Tetanus immunization (to take place after baseline leukapheresis and prior to day 1)
4. 20 mL peripheral blood (red-top tubes) for sera to evaluate baseline antibody responses, and 20 mL peripheral blood (green-top tubes) for CTC baseline evaluation
5. FLT PET/CT scan – to occur within 4 weeks prior to day 1 (up to 6 evaluable patients per cohort)
6. NaF PET/CT scan – to occur within 4 weeks prior to day 1 (max of 10 evaluable patients)
7. Blood for PT/INR for patients undergoing biopsy (may be 30 days up to day of biopsy for patients not taking Coumadin)

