6. Subjects will be observed for additional 30 minutes for unanticipated adverse events.
7. CT scan of abdomen and pelvis (CT of chest as clinically indicated), bone scintigraphy (can be performed +/- 7 days of this visit)

DD. Week 48 Visit (End of Study) (21 +/- 3 days after Week 45 visit):

1. Physical examination, symptoms assessment, and ECOG performance score.
2. Blood draw for CBC, chemistry panel, serum PSA and PAP (can be performed up to 3 days prior to this visit)
3. 10 ml peripheral blood (red-top tubes) for sera to evaluate antibody responses, and 100 ml peripheral blood (green-top heparinized tubes) for T-cell response evaluation and CTC analysis (can be performed +/- 7 days of this visit)
4. CT scan of abdomen and pelvis (CT of chest as clinically indicated), bone scintigraphy (can be performed +/- 7 days of this visit)

EE. 28-Day Follow Up Visit (28 +/- 7 days after Off-study date, if prior to week 48)

Patients will come off study at the time of disease progression, undue toxicity, or at the discretion of the patient and/or treating physician that it is not in the interest of the patient to continue treatment. A separate follow-up visit is not required for patients completing the week 48 evaluation, however for patients coming off study prior to week 48, 28-day follow up visit will include the following:

1. Physical examination, symptoms assessment, and ECOG performance score.
2. Blood draw for CBC, chemistry panel, serum PSA and PAP
3. IF NOT ALREADY COLLECTED WITHIN PREVIOUS 60 DAYS: 10 ml peripheral blood (red-top tubes) for sera to evaluate antibody responses, and 100 ml peripheral blood (green-top heparinized tubes) for T-cell response evaluation and CTC analysis

FF. Long-term Follow-Up

1. Subjects will be contacted by telephone (if not already being seen in clinic) annually for 2 years following the last DNA vaccination to collect clinical information to identify any potential long-term risks. This information has been requested by FDA for all gene delivery trials to assess potential long-term risks. The specific information to be collected annually will include:
 - Date of contact
 - Current medications
 - Hospitalizations (dates and reasons for hospital admission)
 - Stage of prostate cancer, treatments for prostate cancer, and recent serum PSA level
 - New cancer diagnoses
 - New autoimmune disorders
 - New hematologic or neurologic disorders
 - Other new medical diagnoses
 - Date of death if patient deceased

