1. Physical examination, symptoms assessment, and ECOG performance score.
2. Blood draw for CBC, chemistry panel, serum PSA and PAP (can be performed up to 3 days prior to this visit)
3. 10 ml peripheral blood (red-top tubes) for sera to evaluate antibody responses, and 100 ml peripheral blood (green-top heparinized tubes) for T-cell response evaluation and CTC analysis (can be performed \pm 7 days of this visit)
4. CT scan of abdomen and pelvis (CT of chest as clinically indicated), bone scintigraphy (can be performed \pm 7 days of this visit)

PP. 28-Day Follow Up Visit (28 \pm 7 days after Off-study date, if prior to week 48)

Patients will come off study at the time of disease progression, undue toxicity, or at the discretion of the patient and/or treating physician that it is not in the interest of the patient to continue treatment. A separate follow-up visit is not required for patients completing the week 48 evaluation, however for patients coming off study prior to week 48, 28-day follow up visit will include the following:

1. Physical examination, symptoms assessment, and ECOG performance score.
2. Blood draw for CBC, chemistry panel, serum PSA and PAP
3. IF NOT ALREADY COLLECTED WITHIN PREVIOUS 60 DAYS: 10 ml peripheral blood (red-top tubes) for sera to evaluate antibody responses, and 100 ml peripheral

blood (green-top heparinized tubes) for T-cell response evaluation and CTC analysis

4. Patients to remain in telephone contact to report new symptoms up to 90 days after treatment with last dose of pembrolizumab

QQ. Long-term Follow-Up

1. Subjects will be contacted by telephone (if not already being seen in clinic) annually for 2 years following the last DNA vaccination to collect clinical information to identify any potential long-term risks. This information has been requested by FDA for all gene delivery trials to assess potential long-term risks. The specific information to be collected annually will include:
 - Date of contact
 - Current medications
 - Hospitalizations (dates and reasons for hospital admission)
 - Stage of prostate cancer, treatments for prostate cancer, and recent serum PSA level
 - New cancer diagnoses
 - New autoimmune disorders
 - New hematologic or neurologic disorders
 - Other new medical diagnoses
 - Date of death if patient deceased

10. Response Monitoring

A. Safety

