This section outlines the statistical analysis strategy and procedures for the study. Prior to the analysis of the final study data, a detailed Statistical Analysis Plan (SAP) will be written describing all analyses that will be performed.

Summary tabulations will be presented that will display the number of observations, mean, standard deviation, median, range, minimum, and maximum for continuous variables and the number and percent per category for ordinal and categorical data. All endpoints of this study will

be presented graphically where possible using boxplots and histograms for continuous variables and (stacked) bar charts for categorical variables. Data analysis will be performed using SAS[®] (SAS Institute Inc., Cary, North Carolina) version 9.3 or greater.

There are many comparisons made between the two trial arms for multiple measurements, both clinical and laboratory. However, since this a pilot study, no adjustment will be made for multiple comparisons. A two-sided test at a significance level of 0.05 will be used for all comparisons, unless noted otherwise.

F.2. Analysis Populations

The ITT population consists of all patients who are randomized. The per-protocol population consists of all evaluable patients, i.e., patients who have been treated according to protocol (all inclusion/exclusion criteria are satisfied, and adequate treatment compliance (complete treatment to at least day 43). The safety population consists of all subjects who received at least one dose of pTVG HP alone or in combination with pembrolizumab. All primary, secondary and correlative outcomes will be analyzed for both the IIT and per-protocol population. The IIT population will be the primary analysis population. Safety will be evaluated using the safety population.

F.3. Baseline Comparability

All measurements (variables) collected at baseline will be summarized and compared between study arms. These include demographic variables, ECOG PS, lab parameters (CBC, chemistry panel, serum testosterone, PSA and PAP) medical history information and CTCs. Comparisons between study arms of baseline variables on a continuous scale will be performed using a two-sample t-test and/or nonparametric Wilcoxon Rank Sum test. Comparisons between study arms of baseline variables on a categorical scale will be performed using Fisher's exact test.

F.4. Analysis of Primary Endpoints

F.4.1. Analysis of Toxicity Rates and Serum Chemistry Parameters

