Subjects will be evaluated at each visit by a review of systems based on the most recent version of the NCI common toxicity criteria. Furthermore, serum chemistries, including renal function tests, blood counts, liver function tests, and serum amylase, will be evaluated at 6-12 week intervals. Toxicities will be summarized by type and severity in tabular format. Toxicity rates (grade 2, grade 3, grade 4, grade ≥ 2 , grade ≥ 3 , etc.) will be calculated for each study arm and reported along the corresponding 95% confidence intervals. The 95% confidence intervals will be constructed using the Wilson score method. Fisher's exact test will be used to compare toxicity rates between study arms. Serum chemistry and amylase parameters will be summarized using standard descriptive statistics. Changes from the baseline assessment will be evaluated using a paired t-test.

F.4.2. 6-Month Progression Free Survival Rate and Median Time to Radiographic Progression

The 6-month progression-free survival rate, along with the corresponding two-sided 95% confidence intervals, will be reported for each arm, and for the overall combined study. The Wilson

score method will be used to construct the confidence intervals. Fisher's exact test will be used to compare the 6-month progression-free survival rates between study arms.

Median time to radiographic progression will be estimated for each arm using the Kaplan-Meier method. The median time to radiographic progression will be reported for each of the four arms along with the corresponding 95% confidence intervals which will be constructed using the Brookmeyer-Crowley method. The log-rank test will be used to perform the comparison of time to radiographic progression between Arm 1 versus Arm 2. A one-sided 0.10 significance level will be used to conduct the comparison of the 6-month progression-free survival rate and time to radiographic progression between study arms. Within Arm 3 and Arm 4, the null hypothesis that the median time to radiographic progression is at most 3 months will be tested against the alternative hypothesis that the median time to radiographic progression is greater than 3 months.

In order to evaluate the 6-month progression-free rate and median time to radiographic progression as a function of baseline time point (pretreatment or 3-months post treatment, the analysis will be conducted using two different baseline values: (1) Date of randomization, and (2) 3-months disease assessment.

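### After the fourth pembrolizumab dose, the 90-day toxicity window holds 5 calendar toxicity assessments in Arm 1 (4 by the Section 9 text) but 1 in Arm 2, and Arm 2 patients taken off study at Day 169 have no scheduled safety contact for the last 69 days of it

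*Combined protocol and SAP*

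**What the plan says.** **Toxicity window.** Section 8 defines treatment-limiting toxicity as Grade 3 or higher, or a specific Grade 2 event that affects dosing, if at least possibly related. The period ends one month after the final vaccine or "within 90 days of the last treatment with pembrolizumab (whichever is later").

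**Visits in Arms 1 and 2.** The study calendars and Section 9 give both arms the same visits after Day 71: Days 85, 106, 127, 148 and 169, then "9-Month Follow-up (84 days +/- 10 days following 6-month study visit") and a 12-month visit. Dose 4 of pembrolizumab is on Day 64 in Arm 1 (9.K) and Day 148 in Arm 2 (9.P).

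**Patients who leave early.** For anyone off study, Section 6.B keeps the research blood draws: "Patients will continue to have blood drawn for immune studies, as per study calendar, up to one year after screening, even if off study" before then. It also asks for the 6-month evaluations where feasible. It names no later toxicity review or chemistry panel. For Arms 1 and 2 the next stated safety contact is 9.T: "Subjects will be contacted by telephone (if not already being seen in clinic) annually for 2 years following the last DNA vaccination".

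**The extended arms have more.** Sections 9.EE (Arm 3) and 9.PP (Arm 4) each set a "28-Day Follow Up Visit (28 +/- 7 days after Off-study date, if prior to week 48"). Section 9.PP adds, for Arm 4 only: "Patients to remain in telephone contact to report new symptoms up to 90 days after treatment with last dose of pembrolizumab".

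**Analysis.** Section 11.F.4.1 says that Fisher's "exact test will be used to compare toxicity rates between study arms" and does not say over what period. Section 13.A records all adverse events to 30 days after the final dose of study drug, and at least possibly related events at any later time.

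**The concern.** Safety is the first primary objective, and Arms 1 and 2 are the only randomized comparison. The calendar is anchored to Day 1, while the risk period in Section 8 is anchored to the last pembrolizumab dose. Moving pembrolizumab 84 days later (148 − 64) therefore moves Arm 2's risk period into the sparse part of the calendar.

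Leaving study adds to this. Progression is defined only after the 3-month staging, so Day 169 is the first routine scan that can take a patient off study. By Day 169 Arm 1's window has closed, while most of Arm 2's is still open.

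Two things follow. Some Arm 2 patients have no planned safety contact in a period that the protocol itself treats as at risk. And a lower rate of late non-serious events under sequential dosing could partly reflect fewer checks.

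**Working it through.** The plan states no count of post-dose assessments, so there is no figure of its own to reproduce. Its nearest toxicity figures are in Section 11.E: the chance of at least one event in 15 patients. They reproduce and are not disputed: 1 − 0.8^15 = 0.965 and 1 − 0.9^15 = 0.794.

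**Inputs** (nominal days): dose 4 on Day 64 (9.K) and Day 148 (9.P); a 90-day window (Section 8); the toxicity and chemistry rows of the Arm 1 and Arm 2 calendars. Section 9.L lists no symptoms assessment at Day 71, only post-vaccine observation, although the calendar marks one.

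**Step 1, window ends.** Arm 1: 64 + 90 = Day 154. Arm 2: 148 + 90 = Day 238. The vaccine limb of the definition (Day 71 plus about 30 days, so about Day 101) is earlier in both arms, so the 90-day limb governs.

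**Step 2, checks by period** (Arm 1 v Arm 2):

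| Period | Toxicity assessments | Chemistry panels |
|---|---|---|
| 90 days after dose 4 | 5 (Days 71, 85, 106, 127, 148; 4 by text) v 1 (Day 169) | 4 (Days 85, 106, 127, 148) v 1 (Day 169) |
| 30 days after dose 4 (to Day 94 v Day 178) | 2 (Days 71, 85; 1 by text) v 1 | 1 v 1 |
| Day 1 to 90 days after dose 4 | 12 v 11 | 8 v 7 |
| Day 1 to 21 days after dose 4 (Day 85 v Day 169) | 9 v 11 | 5 v 7 |

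**Step 3, visit tolerances.** Month 9 falls between (21 − 3) + (84 − 10) = 92 and (21 + 3) + (84 + 10) = 118 days after Arm 2's dose 4. It is never inside the window, so Arm 2's count is always 1. Arm 1's calendar count ranges from 4 to 6.

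**Step 4, patients off study at Day 169 in Arm 2.** Time left: 238 − 169 = 69 days, and 69/90 = 77% of the window. The next immune draw is at about 169 + 84 = Day 253. The first annual call is at about 71 + 365 = Day 436.

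**Step 5, fewer doses.** If pembrolizumab stops after dose 1, 2 or 3, the calendar counts in the 90 days are 8 v 4, 7 v 3 and 6 v 2. The absolute gap persists, but Arm 2 is better covered.

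**Step 6, dosing wording.** Section 11.C gives Arm 2 pembrolizumab biweekly six times, unlike Sections 6 and 9. On that reading the last dose is at 85 + 5 × 14 = Day 155, and the Arm 2 count is still 1 (Day 169).

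**Step 7, observation time from Day 1.** To 90 days after dose 4: 154 − 1 = 153 v 238 − 1 = 237 days. To 21 days after dose 4: 85 − 1 = 84 v 169 − 1 = 168 days.

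**The case against.** The other side has a good case, and most of it stands as a limit on the consequence.

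- *Section 8 reaches few of these events.* Once dosing has ended, no Grade 2 event can affect pembrolizumab dosing, so the 90-day definition covers essentially Grade 3 and above. This stands.
- *The rule that governs all adverse events is in Section 13.A.* In its 30-day period the arms nearly match. This stands. Section 11.F.4.1 names no period, but it can only tabulate what Section 13.A collects.
- *Whole-arm totals are close.* From Day 1 to 90 days after the last dose they are 12 v 11 and 8 v 7. This narrows the point without removing it, because Arm 2's checks before Day 85 precede any pembrolizumab.
- *Later detection is not lost detection.* Patients still on study have a toxicity review and chemistry at month 9, and the annual call asks about medications, autoimmune disorders and new diagnoses. This stands for persistent events, not for transient or laboratory-only ones.
- *The comparison would hardly move.* With 16 per arm, 2 v 0 events gives a two-sided Fisher p = 0.48, and it takes 5 v 0 to fall below 0.05. This stands for the test. It does not answer the patient-safety gap.

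A reader might infer that serious late toxicity is missed in Arm 2. The documents do not support that: Section 13.E (Table D-2 and its first footnote) makes serious events within 90 days of pembrolizumab reportable in both arms whatever the attribution.

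A reader might also take hypothyroidism as the natural example, since Section 8 lists it as the most frequent immune event (34 of 411). It is a poor one. It usually persists, it is managed without interrupting treatment, and it would usually be found at month 9.

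**Conclusion.** The imbalance is real, and it follows directly from the protocol's own calendar: 5 (4 by text) v 1 toxicity assessments and 4 v 1 chemistry panels in the 90 days after dose 4. Arm 2 patients off study at Day 169 have 69 days with no scheduled safety contact. Arms 1 and 2 lack the off-study visit of Arms 3 and 4 and the telephone contact of Arm 4.

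The consequence is minor. It concerns late, non-serious, mainly transient or laboratory-only events, and their number cannot be derived from the documents. The claim that Arm 2's toxicity rate will be materially understated is therefore not supported.

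The result assumes nominal visit days (Arm 2's count holds at every permitted visit tolerance) and four doses given. How many patients leave at Day 169 is not stated. Not all who progress will: bone-scan-only progression without symptoms or other evidence of progression needs a repeat scan at least 6 weeks later (about 169 + 42 = Day 211, inside the window). Patients thought to be benefiting may also continue (Section 6.B).

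**What to change.** 1. **Section 9, Arms 1 and 2.** Add the Arm 4 telephone contact to 90 days after the last pembrolizumab dose, on or off study. Where that window has passed, add a toxicity review of it, with event dates, at the month-9 or month-12 immune draw or at the annual call.
2. **Section 11.F.4.1.** Report by arm how many patients had the 90-day window actively covered. Add a sensitivity comparison of toxicity limited to the post-dose time actively covered in both arms, that is to 21 days after the last dose. Show observation time beside the rates, because it differs (84 v 168 days from Day 1). The text can go in the analysis plan still to come: "Prior to the analysis of the final study data, a detailed Statistical Analysis Plan (SAP) will be written".

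**Cost.** Item 2 is text only and works although Arms 1 and 2 are closed to accrual. Item 1 is a few calls, or a few questions at contacts already planned, for about 16 patients per arm. The live telephone contact may reach few or none. If the last Arm 2 patient started between May and September 2017 (an assumption; no accrual end date is given), Day 238 fell between late December 2017 and late April 2018. The second annual call (71 + 730 = Day 801) would fall between July and November 2019. A retrospective review carries recall error, and no telephone call recovers laboratory-only events.
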